A Proof of Concept, multi-center, open label, clinical trial addressing the treatment of patients with focal segmental glomerulosclerosis (FSGS) or treatment resistant minimal change disease (TR-MCD). Up to 8 patients with intra-renal tumor necrosis factor (TNF) up-regulation will be treated with 8 weeks of adalimumab therapy. The primary assessment will be of the change in target engagement biomarker levels of urinary TIMP1/Cr or MCP1/Cr from baseline to study week 10. Key secondary outcomes include safety measures, serious adverse events, and adverse events.

Objectives:

This study is proposed to test the hypothesis that FSGS and TR-MCD patients with up-regulation of the TNF pathway can be identified through intra-renal gene expression profiling and assay of urine MCP1/Cr and TIMP1/Cr levels by ELISA.

Furthermore, this study will test the hypothesis that TNF inhibition with adalimumab (Humira) in patients with up-regulation of the intra-renal TNF pathway will result in reduction in urinary MCP1/Cr and/or TIMP1/Cr biomarker levels.

Endpoint

Primary Endpoint: The change in urine MCP1/Cr and TIMP1/Cr levels from baseline to study week 10, i.e. 2 weeks after the final dose of adalimumab

Secondary Endpoints

- (1) Incidence of serious adverse events, adverse events and abnormal laboratory tests
- (2) Percent change of eGFR from baseline to week 10
- (3) Percent change in urine protein:creatinine (UPC) from baseline to week 10
- (4) Proportion of participants achieving a nadir UPC less than 1.5 g/g and at least a 40% reduction from baseline at week 10.

Exploratory Endpoints

- (1) Correlation coefficient between intra-renal gene expression of TNF and urinary MCP1/Cr and TIMP1/Cr biomarker levels at baseline
- (2) Time to reduction of urinary MCP1/Cr and TIMP1/Cr biomarkers from baseline
- (3) Change in urinary EGF biomarker levels between baseline and week 10
- (4) Change in Quality of Life score between baseline and week 10.

Population:

Up to eight patients with kidney biopsy confirmed FSGS or TR- MCD, increased urinary excretion of biomarkers of TNF activation (MCP1/Cr and TIMP1/Cr) at study screening, eGFR>30 ml/min/1.73 m² at enrollment, urine protein:creatinine (UPC) ratio ≥1.5 g/g at enrollment, age between

6-80 years, inclusive, and stable therapy with angiotensin converting

enzyme inhibitors, angiotensin receptor blockers, and oral

immunosuppression agents for at least 30 days prior to enrollment will be enrolled and entered into the intervention phase of the study. Additional eligibility criteria are listed in the inclusion and exclusion criteria section

below.

Phase: Proof of Concept/Phase 1b/2a

Number of Sites enrolling participants:

Up to 8 sites in the USA will participate in this study.

Humira, adalimumab

Description of Study Manufactured by Abbvie

Agent: Subcutaneous

A total of 5 doses will be administered during the trial at weeks 0, 2, 4, 6 and 8. Dosing will be based on weight:

	0
Subject Weight	Adalimumab dose every other week
15kg to <30kg	20mg
≥30kg	40mg

Study Duration:

Approximately 14 months

- 1. 7 month enrollment phase
- 2. 2 week screening, 8 week intervention and 6 week post intervention observation period for a total of 14 week participation per patient
- 3. 3 month analysis phase

Participant Duration:

16 weeks

- 1. 2 week screening period
- 2. 8 week intervention period
- 3. 6 week follow up post treatment

SCHEMATIC OF STUDY DESIGN

Figure 1. Schematic of Study Design

TEB = Target Engagement Biomarker

TEB levels will be assessed at study weeks -2, 0, 2, 8, and 10

2 INTRODUCTION: BACKGROUND INFORMATION AND SCIENTIFIC RATIONALE

2.1 BACKGROUND INFORMATION

FSGS is a pattern of kidney injury that manifests as isolated, asymptomatic proteinuria or nephrotic syndrome. It is a serious condition and may lead to kidney failure in up to 50% of patients over a five to ten year period. Although primary FSGS is a rare entity, the incidence of the disease has been steadily rising over the last 30 years and it is generally the most common form of primary glomerular disease in all patient subgroups. Moreover, it one of the leading causes of chronic and end-stage kidney disease (ESKD), accounting for 5% of adult and 12% of pediatric ESRD cases.

The first-line therapy for primary FSGS, especially in those with nephrotic-range proteinuria, is usually corticosteroids. In patients who are unresponsive to steroids, calcineurin inhibitors (CNIs) are the recommended second-line therapy according to current KDIGO clinical guidelines¹. Overall, approximately 20% of patients with FSGS will have a favorable response to corticosteroids and up to 40% will have clinical benefit from treatment with a calcineurin inhibitor. Other agents that have been tried with marginal success include mycophenolate mofetil and rituximab. Patients with treatment-resistant FSGS are at higher risk of progressing to ESKD.

Adjuvant therapies designed to reduce proteinuria in primary FSGS are mainly focused on agents that inhibit renin-angiotensin system including angiotensin-converting enzyme inhibitors (ACEIs), angiotensin II receptor blockers (ARBs), or aldosterone antagonists. This is based on evidence that reduction in proteinuria in response to treatment is renoprotective and an independent predictor of kidney survival. These clinical data underscore the limitations of current therapy for FSGS and highlight the need to develop new strategies to safely and effectively achieve a reduction in proteinuria, either a partial or complete remission, preservation of kidney function and minimization of the adverse effects due to reduction of exposure to agents with little expectation of efficacy.

While there are many insults that result in FSGS, molecular profiling can result in identifiable subgroups of affected patients with discrete pathophysiological mechanisms that may inform a precision medicine driven next generation of treatment strategies for individuals with FSGS and treatment resistant MCD.

2.2 RATIONALE

Based on molecular profiling, informed therapy selection targeting the underlying disturbance has been used successfully in health care and biomedical research. When successful, this forms the basis of precision medicine for the treatment of selected patient populations.

The Nephrotic Syndrome Study Network (NEPTUNE, PI [name]) study investigators have used genome wide expression profiles of renal biopsy specimens available from more than 250 patients to identify molecular subgroups of NS². Three distinct patient subgroups were identified and associated with long-term outcomes. Molecular pathway analysis of the subgroups with TR-MCD and FSGS showed activation of TNF as defined by causal inference network analysis of established downstream pathway members, including TIMP1 and MCP1 in one of the 3 subgroups. These patients presented with higher levels of proteinuria, lower levels of GFR, and more rapid progression of their glomerular disease. A TNF Z-score was computed for each NEPTUNE participant with MCD and FSGS. The score is the average Z-score of gene expression level across 145 TNF pathway genes from the tubulointerstitial compartment

of each participant's renal biopsy. Urinary MCP1 and TIMP1 were measured by ELISA from their baseline study visit and normalized to urine creatinine. Correlations of TNF gene expression Z-score with urinary biomarkers are shown in Figure 1 and distributions of these measures in boxplots from TNF z-score < 0 vs > 0 are plotted in Figure 2.

Figure 2: Scatter plot of TNF z- score and urinary TIMP1/Cr, A: All FSGS and MCD patients (corr = 0.47, P<0.001) TNF z-score and urinary MCP1/Cr, B: All FSGS and MCD patients (corr = 0.51, P<0.001) TNF z-score and urinary TIMP1/Cr ng/mg. (L. Mariani, et al 2017)

[figure not shown]
[figure not shown]

Figure 3: Distribution of biomarker level by TNF Z-score category. Difference in means was statistically significant (TIMP1, p-value 0.009; MCP1 p-value 0.001) (L. Mariani, et al 2017)

A logistic model was fit with the outcome of TNF Z-score >0 to assess the predictive ability of urinary biomarkers individually and combined. Results are shown in Table 1 for the subgroup of participants with eGFR >45. Model 3, which included both biomarkers as predictors had the highest positive predictive value and correct classification. Correctly classified was calculated by assigning those with an estimated probability of disease >= 50% as having disease and then calculating the % that are correctly classified as having and not having disease (true TNF Z-score > vs <= 0) using a patient sample with eGFR > 45 and either FSGS or MCD.

participants with editives								
	Model 1 c-statistic 0.79		Mod	del 2	Mod	el 3		
Patients with eGFR >45			c-statis	tic 0.79	c-statist	tic 0.82		
(n = 49; 13 Events)	PPV 33%		PPV	67%	PPV	75%		
	correctly classified 69%		Correctly cla	assified 78%	Correctly Cla	ssified 82%		
	OR P-value		OR	P-value	OR	P-value		
Log2(uTIMP/Cr)	1.79	0.017			1.54	0.07		
Log2(uMCP/Cr)			2.31	0.008	1.81	0.08		

Table 1: Results of Multivariable Logistic Models of TNF Z-score >0 in NEPTUNE FSGS and MCD participants with eGFR>45

Because both biomarkers contributed to greater predictive accuracy, both will be measured for patient selection into the clinical trial. The coefficients from the multivariable model will be used to calculate the odds of having a TNF Z-score >0 for each person. Odds are then converted to probability and patients with a probability >= 50% of having a positive TNF Z-score would be eligible for enrollment. Mathematically, the following equations will be used to calculate the probabilities for study inclusion:

- 1. Constant + [log2(uTIMP1/Cr) * Coef1] + [log2(uMCP1/Cr) * Coef2] = log Odds
- 2. Exp(log Odds) = Odds
- 3. Probability = Odds / (1 + Odds)

Using the following coefficients and constant from Model 3 in Table 2:

Logistic regression	Number of obs	=	49
	LR chi2(2)	=	13.61
	Prob > chi2	=	0.0011
Log likelihood = -21.542865	Pseudo R2	=	0.2401

tnf_cat	Coef.	Std. Err.	Z	P> z	[95% Conf.	Interval]
logMCPI_uCR_ngmg	.59214	.3381858	1.75	0.080	0706919	1.254972
log2timp1_uCr_ngmg	.4325066	.2401973	1.80	0.072	0382715	.9032848
cons	-1.001269	.5091692	-1.97	0.049	-1.999222	0033157

i.e., $\log Odds = -1.001269 + 0.59214 * \log 2(uTIMP1/Cr) + 0.4325066 * \log 2(uMCP1/Cr)$.

In NEPTUNE, these molecular pathway-defined patient subgroups characterized by high intra-renal TNF activation have documented persistence in proteinuria and reduced kidney function during prospective observation. Past studies of TNF inhibition in unselected treatment resistant FSGS patients demonstrated a reduction in proteinuria and preservation of estimated glomerular filtration rate (eGFR) in approximately 25% of studied patients³. In the FONT study, there were no clinical or laboratory findings that predicted response patterns to TNF-inhibition. This study also identified the accelerated clearance of the TNF monoclonal antibody in this patient population with significant proteinuria ⁴⁻⁶. On average the Area Under the Curve (AUC) was 50% lower than that of comparison populations without proteinuria. In a parallel study of a small therapeutic compound, similar reduction in AUC in proteinuric patients with FSGS was documented suggesting that both large and small molecules are cleared more rapidly in patients with proteinuric kidney diseases such as FSGS and TR-MCD⁷. The recent findings within the NEPTUNE investigative community suggest that we may now have a mechanism to identify TNF-target relevant patients with primary nephrotic syndrome and use prior evidence to select a likely drug dosing regimen for this patient population.

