## 1. Introduction

#### 1.1 Preface

This Statistical Analysis Plan (SAP) describes statistical methods and analyses for the Precision Medicine Guided Use of TNF Inhibition in FSGS and Treatment Resistant Minimal Change Disease: Proof of Concept Target Engagement Study. This document should be read in tandem with the Precision Medicine Guided Use of TNF Inhibition in FSGS and Treatment Resistant Minimal Change Disease: Proof of Concept Target Engagement Study Protocol version 5.0, dated February 21, 2023. The SAP was finalized prior to the database lock.

The trial proposes to investigate whether urinary markers of intra-renal tumor necrosis factor (TNF) pathway activation in patients with focal segmental glomerulosclerosis (FSGS) or treatment resistant- minimal change disease (TR-MCD) are reduced with TNF inhibition via adalimumab.

[figure not shown]
This proof-of-concept, multi-center, open-label clinical trial addresses the treatment of patients with clinically active FSGS or TR-MCD and urinary biomarkers of intra-renal TNF up-regulation, including urinary monocyte chemoattractant protein 1/urinary creatinine (urinary MCP1/uCr) and urinary tissue inhibitor of metalloproteinase 1/urinary creatinine (urinary TIMP1/uCr). These biomarkers have been shown to indicate intra-renal TNF upregulation. Up to eight patients, aged 6-80 years, were treated with 8 weeks of adalimumab therapy to assure a minimum evaluable study sample of six patients in this single-arm study. Adalimumab was dosed based on weight and administered subcutaneously every two weeks for 8 weeks (5 total doses). The urinary biomarkers MCP1/uCr and TIMP1/uCr were assessed throughout the study. The primary endpoints are the change in target engagement biomarker levels of urinary TIMP1/uCr and MCP1/uCr from baseline to study week 10. Key secondary outcomes include safety measures, serious adverse events, adverse events, percent change of estimated glomerular filtration rate (eGFR) and urine protein to creatinine ratio (UPCR) from baseline to week 10, and proportion of participants achieving a nadir UPCR less than 1.5 g/g and at least a 40% reduction from baseline at week 10.

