# 3. Study Aims and Hypotheses

## 3.1 Primary Aim and Hypothesis

The primary purpose of this proof-of-concept study is to test the hypothesis that TNF inhibition with adalimumab (Humira) in patients with up-regulation of the intra-renal TNF pathway results in reduction in urinary indicators of TNF pathway activation, specifically urinary MCP1/uCr or TIMP1/uCr levels.

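### Model 3's 75% PPV is 6 of 8 flagged patients, apparently in-sample and with no interval, yet the treated group is described as having TNF up-regulation

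*Protocol*

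**What the plan says.** Protocol 2.2 (Rationale) fits three logistic models for TNF Z-score above 0 in 49 NEPTUNE participants, 13 of them events. It prefers the two-marker model: "Model 3, which included both biomarkers as predictors had the highest positive predictive value and correct classification". Correct classification was computed by "assigning those with an estimated probability of disease >= 50% as having disease", "using a patient sample with eGFR > 45 and either FSGS or MCD". The same cut-off becomes the entry rule: "patients with a probability >= 50% of having a positive TNF Z-score would be eligible for enrollment". The section describes no hold-out sample, cross-validation or bootstrap, and gives no interval for PPV or correct classification.

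Elsewhere the treated group is described as having the property that the model predicts. The Précis in the Protocol Summary says "Up to 8 patients with intra-renal tumor necrosis factor (TNF) up-regulation will be treated with 8 weeks of adalimumab therapy". SAP 1.1 says of the two markers "These biomarkers have been shown to indicate intra-renal TNF upregulation". SAP 3.1 states the primary hypothesis as "TNF inhibition with adalimumab (Humira) in patients with up-regulation of the intra-renal TNF pathway results in reduction in urinary indicators".

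SAP 10, item 1, drops the hypothesis that such patients can be identified, and treats completion of screening as its demonstration.

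**The concern.** A PPV computed in the sample that produced the coefficients tends to be optimistic, and one based on a handful of flagged patients is imprecise. The PPV matters here because the primary hypothesis concerns patients with intra-renal up-regulation, while patients enter on a prediction of it. If some treated patients lack the property, a flat or mixed biomarker response has two possible explanations: the drug did not act on the pathway, or some of the patients were not the intended ones. Without the PPV and its uncertainty beside the primary result, a reader cannot weigh one against the other. Completing screening does not help, because passing a model's cut-off is not evidence that the model classifies correctly.

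**Working it through.** **Inputs (all Protocol 2.2).** n = 49, 13 events, so 36 non-events. Model 3: PPV 75%, correctly classified 82%. Model 2: 67% and 78%. Model 1: 33% and 69%. Cut-off: predicted probability of at least 50%. Model output: "Log likelihood = -21.542865", LR chi-square 13.61, pseudo R² 0.2401.

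**Step 1: reproduce the fit.** Null log likelihood = 13·ln(13/49) + 36·ln(36/49) = −28.348. LR = 2 × (28.348 − 21.543) = 13.61. Pseudo R² = 1 − 21.543/28.348 = 0.240. Both match, so the output belongs to the 49-patient sample with 13 events.

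**Step 2: recover the two-by-two table for Model 3.** Only 40/49 = 81.6% rounds to 82%, because 39/49 is 79.6% and 41/49 is 83.7%. So TP + (36 − FP) = 40, which gives TP = FP + 4. Then PPV = (FP + 4)/(2·FP + 4). FP = 1 gives 5/6 = 83%, FP = 2 gives 6/8 = 75%, and FP = 3 gives 7/10 = 70%. Only FP = 2 fits.

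| | Z > 0 | Z ≤ 0 | Total |
|---|---|---|---|
| Flagged | 6 | 2 | 8 |
| Not flagged | 7 | 34 | 41 |
| Total | 13 | 36 | 49 |

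By the same method Model 2 is TP 4, FP 2 (38/49 correct) and Model 1 is TP 2, FP 4 (34/49 correct). Model 3's lead over Model 2 is two patients.

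**Step 3: precision (exact Clopper-Pearson 95% intervals).**
- PPV 6/8 = 75% (34.9% to 96.8%)
- Correct classification 40/49 = 81.6% (68.0% to 91.2%)
- Sensitivity 6/13 = 46% (19% to 75%)
- Specificity 34/36 = 94% (81% to 99%)
- Calling all 49 negative: 36/49 = 73.5% correct, inside the interval for Model 3

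**Step 4: what the protocol's own PPV implies for 8 treated patients.** Expected number without Z > 0 = 8 × 0.25 = 2. Probability that all 8 have it = 0.75⁸ = 0.10. Across the interval, the expected number with it runs from 8 × 0.349 = 2.8 to 8 × 0.968 = 7.7.

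**Step 5: two influences on the PPV in the trial, in opposite directions.**
- *Optimism lowers it.* Heuristic shrinkage = (13.61 − 2)/13.61 = 0.85. In a simulation that assumes two equally strong bivariate-normal markers, true c-statistic 0.76 to 0.82, correlation 0.2 to 0.6 and 13/49 events, in-sample PPV exceeds new-sample PPV by about 3 to 6 points on average. None of those assumptions is a document figure.
- *Higher prevalence raises it.* PPV = se·π / [se·π + (1 − sp)(1 − π)] with se = 6/13 and sp = 34/36 held fixed. This gives 59% at π = 15%, 75% at 26.5% (13/49), 85% at 40% and 89% at 50%. The trial requires UPC of at least 1.5 g/g, admits eGFR above 30 (the model used above 45) and takes only steroid-resistant MCD. Protocol 2.2 says the TNF subgroup had higher proteinuria and lower GFR.

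**Step 6: which rule the figures describe.** exp(0.59214) = 1.81 and exp(0.4325066) = 1.54. The output table attaches these coefficients to MCP1 and TIMP1 respectively, and Table 1 gives the same odds ratios for the same markers. The printed eligibility equation attaches 0.59214 to TIMP1 and 0.4325066 to MCP1. If that equation was used for screening, neither the 75% nor the 82% describes the rule applied.

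**The case against.** The strongest reply is that the documents never project a number of up-regulated patients from the 75%. Protocol 4.1 says only that biomarker levels indicate up-regulation, and 2.2 states the 50% rule openly. The study is descriptive, and SAP 7.6 rests inference on the size of effects. SAP 8.3 and 9.4 tabulate the TNF activation score and correlate it with both markers. SAP 6.1 rests the link between markers and activation on a 2023 publication that may contain validation and cannot be seen here. Patients have already been treated, so rewording changes no design decision.

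Much of this stands. The conflict between the label and the 75% exists with or without optimism. The sentence in SAP 1.1 cannot be called wrong without its source. The tissue check is real but partial, since it covers only participants with a biopsy within 12 months. The unqualified wording in the Précis and SAP 3.1 remains, as does the missing interval.

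A reader might go further and infer that the true PPV is 0.55 to 0.69, that about a third of patients lack the target, and that power collapses. The documents do not support this:
- That PPV range comes from assumed marker SDs of 1.5 to 2.0 and correlations of 0.3 to 0.5. Under those inputs even a rule with known coefficients reaches only 0.62 to 0.70, so most of the gap from 0.75 is not overfitting.
- It fixes prevalence near 13/49, which the trial's entry criteria may raise.
- The power figures are 72% falling to 40% at PPV 0.75 (7 patients, effect size 1.2, exact signed-rank test at 0.05). They assume exactly no response at Z ≤ 0, but Z is a continuous average over 145 genes and 0 is only a cut-point.

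**Conclusion.** The point holds in a limited form. Model 3's PPV is 6/8, with an exact 95% interval of 35% to 97%, and its sensitivity is 6/13. Both are unvalidated in the documents. That they are in-sample is the natural reading of 2.2, although the text does not use the term. Describing all treated patients as having up-regulation is inconsistent with the protocol's own figure, which implies about 2 of 8 without it and a 10% chance that all 8 have it. These two numbers take the 75% at face value and treat patients as independent.

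No net direction or size of error in the PPV should be claimed for the trial population, because optimism and prevalence pull in opposite ways and the documents fix neither. The exchanged coefficients come first, since they decide which rule any performance figure belongs to.

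**What to change.** 1. Reconcile the printed equation in Protocol 2.2 with the output table and the Table 1 odds ratios, and state which equation was used for screening.
2. In 2.2, report the PPV, sensitivity and c-statistic of the rule actually applied, with 95% intervals. Add a bootstrap optimism correction from the existing NEPTUNE data: refit in each resample, apply the 50% cut-off, and compare with performance in the 49 originals. If the exchanged equation was used, each refit must carry the same exchange.
3. In the Précis, Protocol 4.1 and SAP 1.1 and 3.1, describe the population as patients with a model-predicted probability of TNF Z-score above 0 of at least 50%.
4. Interpret the primary result for that population, with the PPV and its interval beside it.

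The cost is a short re-analysis of data already held and some rewording. The stated performance will probably look less favourable. No new patients or samples are needed.

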5.3 STRATEGIES FOR RECRUITMENT AND RETENTION

Patients will be recruited from the active population of patients with FSGS or TR-MCD w at participating sites. TR-MCD is defined as persistent proteinuria despite treatment. Following informed consent and when appropriate, assent, a screening visit will be conducted. Patients with elevated TIMP1/Cr and MCP1/Cr levels and meeting all other eligibility criteria will be scheduled to receive adalimumab every two weeks for 8 weeks (5 total doses). It is anticipated that only 25% of screened patients will be eligible for study participation based on TIMP1/Cr and MCP1/Cr levels. Eight eligible patients will begin study intervention with a goal to have a minimum of 6 patients fully completing the intervention phase and therefore contributing to the final analysis of the primary endpoint after 5 doses of adalimumab over an 8 week period.

Patients will be compensated for study participation to offset costs related to travel to study visits and incidentals.

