#### 1. Change in the primary aim and hypothesis

Exclusion of the hypothesis that FSGS patients with up-regulation of the TNF pathway can be identified through intra-renal gene expression profiling and assay of urinary MCP1/uCr and urinary TIMP1/uCr levels by ELISA. This is demonstrated by the successful completion of the screening protocol that determined if they were included/eligible for drug.

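### The enrolment equation printed in Protocol 2.2 swaps the MCP1 and TIMP1 coefficients of the model it is taken from

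*Protocol*

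**What the plan says.** Protocol 2.2 fits logistic models for a TNF Z-score above 0 in 49 participants of the earlier cohort (13 events, eGFR above 45). It selects Model 3, which contains both urinary markers, and sets the rule that "patients with a probability >= 50% of having a positive TNF Z-score would be eligible for enrollment". It says that its equations will supply the probabilities for study inclusion.

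The section gives the Model 3 coefficients in three places:

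- **Regression output:** "logMCPI_uCR_ngmg .59214 .3381858 1.75 0.080" and "log2timp1_uCr_ngmg .4325066 .2401973 1.80 0.072".
- **Table 1, Model 3:** odds ratio 1.81 (P 0.08) for MCP1 and 1.54 (P 0.07) for TIMP1.
- **Written-out equation:** constant -1.001269, then "0.59214 * \log 2(uTIMP1/Cr) + 0.4325066 * \log 2(uMCP1/Cr").

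Inclusion criterion 3 (Protocol 5.1, SAP 5.2.1) asks only for increased excretion and gives no cut-off. SAP 6.1 says that no reference ranges are published. The score in Protocol 2.2 is therefore the only numeric biomarker rule in either document. SAP section 10 lists four changes, and none of them touches the equation.

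**The concern.** The output and Table 1 assign the larger coefficient to MCP1; the equation assigns it to TIMP1. Both cannot describe the same model, and the equation is the line that someone doing the screening calculation would copy.

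If the printed line was used, some patients with relatively high TIMP1 were admitted with a fitted probability below 50%. Some with relatively high MCP1 were turned away although they reached it. The reported positive predictive value of 75% and correct classification of 82% would not describe the rule applied.

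At most eight patients are treated, and they are chosen because the score indicates TNF activation. One or two admitted by the wrong formula would change what the treated group represents. SAP section 10, change 1, also drops the hypothesis that such patients can be identified, on the ground that "This is demonstrated by the successful completion of the screening protocol that determined if they were included/eligible for drug". That reasoning presupposes that screening applied the intended score.

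**Working it through.** **1. Which assignment belongs to Model 3.** The inputs are the coefficients, standard errors and log likelihood in the Protocol 2.2 output. OR = exp(coefficient), z = coefficient / SE, P two-sided normal.

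| Output row | Coefficient | SE | OR | z | P | Table 1 |
|---|---|---|---|---|---|---|
| MCP1 | 0.59214 | 0.3381858 | 1.808 | 1.751 | 0.080 | 1.81, P 0.08 |
| TIMP1 | 0.4325066 | 0.2401973 | 1.541 | 1.801 | 0.072 | 1.54, P 0.07 |

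The overall fit also reproduces:

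- Null log likelihood for 13 of 49: 13 ln(13/49) + 36 ln(36/49) = -28.348.
- LR chi-square: 2 x (28.348 - 21.543) = 13.61.
- Pseudo-R2: 1 - 21.543/28.348 = 0.240.

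The output is coherent and agrees with Table 1 on labels, odds ratios and P values. Only the equation disagrees, since it implies odds ratios of 1.81 for TIMP1 and 1.54 for MCP1. Broken table text cannot explain this: the equation is a separate line, and the two tables confirm each other. A plausible cause is that the generic formula lists TIMP1 first while the output lists MCP1 first.

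**2. Effect on the score.** No assumption is needed here. Printed minus fitted log odds = (0.59214 - 0.4325066) x [log2(TIMP1/Cr) - log2(MCP1/Cr)] = 0.1596 x the difference. The two versions agree only when the ratios are equal. A probability of 50% means log odds of 0, so the boundaries cross where both log2 values equal 1.001269 / (0.59214 + 0.4325066) = 0.977, i.e. 1.97 ng/mg.

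TIMP1/Cr needed to qualify:

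| MCP1/Cr (ng/mg) | Fitted | Printed |
|---|---|---|
| 1 | 2^(1.001269/0.4325066) = 4.98 | 2^(1.001269/0.59214) = 3.23 |
| 4 | 2^((1.001269 - 1.18428)/0.4325066) = 0.75 | 2^((1.001269 - 0.8650132)/0.59214) = 1.17 |

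Two example patients:

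- TIMP1/Cr 4, MCP1/Cr 1. Fitted log odds -1.001269 + 2 x 0.4325066 = -0.136, or 46.6%. Printed log odds -1.001269 + 2 x 0.59214 = 0.183, or 54.6%.
- TIMP1/Cr 1, MCP1/Cr 4. Fitted 54.6%, printed 46.6%.

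**3. How many patients.** The documents give no joint distribution of the markers, so this step rests on assumptions: bivariate normal log2 values, equal SDs of 1 to 2, correlation 0.3 to 0.6. Levels are set so that 25% pass under one equation or the other. That pass rate is the protocol's own expectation (section 5.3: "It is anticipated that only 25% of screened patients will be eligible for study participation based on TIMP1/Cr and MCP1/Cr levels").

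| Difference in mean log2 level | Screened patients changing status | Printed passes below 50% fitted |
|---|---|---|
| 0 | 4-6% | 7.9-11.5% |
| up to 1 unit either way | 4-8% | 1-26% |
| up to 3 units either way | 4-21% | 0-58% |

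With equal means, 8 x 0.079 = 0.6 to 8 x 0.115 = 0.9 of eight treated patients would fall below 50%. The extreme of 58% (8 x 0.58 = 4.6 patients) comes from a single corner: SD 1, correlation 0.3, TIMP1 eight-fold higher on average, and 25% passing as printed.

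**The case against.** The contradiction itself is not in dispute; the case against concerns its weight.

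- **The harm is conditional.** Nothing shows that the printed line was ever used. SAP 1.1 describes treatment in the past tense, so a correction cannot alter who was enrolled, and the primary test is a within-patient comparison without the score. This stands, and limits the consequence to who was selected and how that is reported.
- **The model is imprecise.** It has 13 events, and both coefficient intervals include zero. The coefficients differ by 0.16, about 0.38 standard errors if their covariance is taken as zero (it is not given). The stated 75% and 82% correspond to 6 of 8 predicted positives being correct and 40 of 49 classified correctly. The exact 95% interval for 6/8 is about 35-97%. So misclassified means departing from the protocol's own rule, not shown to be wrong about TNF activation. This also stands, but an imprecise model does not excuse applying a different equation from the one fitted.
- **The widest range reflects the chosen grid.** Agreed; 58% should carry little weight. Equal SDs are also doubtful. The SE ratio of 0.3382/0.2402 = 1.41 suggests that TIMP1 is more spread or that the scales differ. With that SD ratio and equal means, the share of printed passes below 50% is 10-15%.
- **The log base of the MCP1 row is unclear.** Its name lacks the 2 that the TIMP1 name carries, and 1.41 is close to 1/ln 2 = 1.44. Table 1 and the generic formula both say log2, which supports the corrected equation, but the base should be confirmed.
- **Completing screening would not prove the identification hypothesis under either equation.** True, and a separate weakness of the SAP. The swap adds doubt about what was completed.

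**Conclusion.** The concern holds. The equation in Protocol 2.2 attaches each Model 3 coefficient to the wrong marker; this follows from the protocol's own figures without any assumption. It matters because this is the only numeric biomarker rule for entry and neither document corrects it.

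The effect is confined to patients between the two 50% boundaries. Those with equal markers, or with both clearly high or both clearly low, are classified alike. Under the equal-mean, equal-SD assumption fewer than one of eight treated patients would be affected. Larger numbers require the markers to differ markedly in average level, which the documents neither support nor exclude. Whether anyone was in fact misclassified depends on which version was run, and only the investigators can say.

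**What to change.** 1. Correct the equation in Protocol 2.2 to log Odds = -1.001269 + 0.4325066 x log2(uTIMP1/Cr) + 0.59214 x log2(uMCP1/Cr), after confirming from the model-fitting file that the MCP1 variable is on the log2 scale.
2. State in the SAP or study report which version the screening calculation used.
3. If it was the fitted version, say so; nothing further is needed.
4. If it was the printed version, recompute every screened patient's probability from the stored screening values. Report how many treated patients fall below 50% and how many excluded patients reach it, and qualify the statement in SAP section 10, change 1.

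The cost is one corrected line and one sentence, plus a short recalculation from existing data if the printed version was used.
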